Bacterial Questionnaires: At the home visit we may collect data on established risk factors for acquisition of *S. aureus* and other bacteria, such as daycare, gym use, and antibiotic use, and household location (which will be collected on a separate form, then geocoded into X, Y coordinates from address data before linkage with health or demographic data).

Pet Questionnaire: We may collect data on participant contact with and characteristics of pet animals in the home. These data will include notations from visual inspection of the pets and areas of the house related to pets (e.g. pet crates).

Sampling of pets and pests: Under an approved ACUC protocol ([name], SP14H352, 9/18/2014-9/18/2017), Copan Eswabs™ (Copan Diagnostics, Murrieta, CA) for bacterial culture and Catch-All™ sample collection swabs (Epicentre Biotechnologies, Madison, WI) for bacterial community analysis may be collected from all pet animals at multiple anatomical sites and from freshly trapped rodents and other trapped pests. The informed consent process for these pet swabs will be conducted under the approved ACUC protocol and conducted by the [name] group. Study participants randomized to pest control will be given a magnet with a number to call to schedule optional pick-up of freshly trapped rodents and other pests from the home to transport to the laboratory for bacterial sampling.

Particulate Matter and Airborne Animal Allergens: Particulate matter monitoring will be conducted in the child's bedroom using integrated sampling direct-reading methods for an approximate 5 day period. Air samples for PM_{2.5} and PM₁₀ will be collected using methods developed during previous childhood asthma studies.⁽³⁴⁾ After gravimetric analysis, the PM₁₀ filters will be assayed for allergen content in the [name] laboratory. PM₁₀ samples will be analyzed because previous research indicates that the bulk of airborne animal allergens is contained on particles less than 10µm in aerodynamic diameter.^(35, 36) Microbial air sample measurements may be obtained.

Inspirotec air monitors will be deployed in a subset of homes to establish correlation between our PM10 measurements of airborne biomass and Inspirotec spectroscopic measurements of biomass. We will also compare the limits of detection of the two methods and validate the utility of the Inspirotec sampler as easily deployable in home environments.

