The intervention being tested is the environmental intervention, but all participants will receive asthma medication based on national guidelines. All will receive a short-acting beta agonist, albuterol, for use as a reliever medication. All participants, at least at the start of the study, will also receive a controller medication, Flovent or Advair or an equivalent alternative medication.

- b. Justification and safety information if FDA approved drugs will be administered for non-FDA approved indications or if doses or routes of administration or participant populations are changed. N/A

Justification and safety information if non-FDA approved drugs without an IND will be administered. NA

6. Study Statistics

- a. Primary outcome variable. The primary outcome variable is the treatment step that the participant is assigned at the 6 month clinic visit (see treatment algorithm above).

- b. Secondary outcome variables.

Secondary outcomes include: (1) daily inhaled corticosteroid dose, (2) allergic inflammation markers (allergen-specific IgE, FENO, (3) measures of asthma control (days of short-acting beta agonist use, days of slowed activity due to asthma, days of exercise-induced symptoms, days of cough without an upper respiratory infection, nights of waking due to asthma symptoms), and (4) measures of exacerbations (oral corticosteroid bursts, hospitalizations, emergency department visits, and unscheduled physician visits). Other secondary outcomes include FEV1/FVC, % change in FEV1 after albuterol, and asthma severity, as measured by the CASI.⁽²⁹⁾

- c. Statistical plan including sample size justification and interim data analysis.

Power Estimate

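### In the Inspirotec sub-study the only stated analysis of the paired readings is a correlation, which cannot show how well the sampler reproduces the PM10-based measure

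*Combined protocol and SAP*

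**What the plan says.** The sampler is described in two sentences under Particulate Matter and Airborne Animal Allergens, in part a of Study Procedures. On the sample, the text says that "Inspirotec air monitors will be deployed in a subset of homes". It gives no number of homes, no selection rule and no indication of which visits or arms are covered.

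Three aims follow:

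- The first concerns the paired readings: "to establish correlation between our PM10 measurements of airborne biomass and Inspirotec spectroscopic measurements of biomass".
- The second is to "compare the limits of detection of the two methods".
- The third is to "validate the utility of the Inspirotec sampler as easily deployable in home environments".

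The paragraph before describes the reference samples: "After gravimetric analysis, the PM₁₀ filters will be assayed for allergen content". No unit is given for biomass by either method. The Analysis Plan in section 6 (Study Statistics) contains nothing on the sampler: no bias, agreement or calibration analysis, no target correlation and no acceptance limit.

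**The concern.** The sub-study sets two methods side by side for one named quantity, airborne biomass. The useful questions about such pairs are whether the new method is shifted, whether it compresses or stretches differences, and how far a single home's reading can be trusted. A correlation answers none of these directly. It is unchanged when one method is multiplied by a constant. On the log scale it is also unchanged when differences are compressed, provided the error shrinks in proportion. For a fixed measurement error it rises as homes differ more.

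The detection-limit comparison does not fill the gap, because it says nothing about bias above the limit. What is at stake is what this ancillary comparison can conclude about the sampler. No trial outcome depends on it.

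**Working it through.** **Inputs.** The plan gives no sample size, unit, error variance or target for this comparison, so it has no figure to reproduce. Every SD and bias below is an assumption chosen to show how correlation behaves.

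**Model (log scale).** PM10-based reading X = T + e1; Inspirotec reading Y = a + bT + e2. T is the true level, centred at 0, with between-home SD sT. The independent errors have SDs s1 and s2.

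- r = b·sT² / √[(sT² + s1²)(b²·sT² + s2²)]. The shift a does not appear.
- 95% limits for the ratio Y/X = exp{a ± 1.96·√[(b−1)²·sT² + s1² + s2²]}.
- Lin's concordance coefficient = 2b·sT² / (var X + var Y + a²).

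**Step 1: equal error in both methods, no bias.** Here r = sT²/(sT² + s²), and the limits are a factor of exp(1.96·√2·s) either way.

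- sT = 1, s = 0.5: r = 1/1.25 = 0.80; factor exp(1.386) = 4.0.
- sT = 1, s = 0.35: r = 1/1.1225 = 0.89; factor exp(0.970) = 2.6.

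**Step 2: bias (sT = 1, s1 = 0.2).**

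| Case | r | Concordance | 95% ratio limits |
|---|---|---|---|
| No bias, s2 = 0.2 | 0.96 | 0.96 | 0.57 to 1.74 |
| Constant two-fold over-read (a = ln 2), s2 = 0.2 | 0.96 | 0.78 | 1.15 to 3.48 |
| Slope b = 0.5, s2 = 0.1 | 0.96 | 0.77 | 0.34 to 2.93 |

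For the first row, r = 1/√(1.04 × 1.04) = 0.96. For the third, r = 0.5/√(1.04 × 0.26) = 0.96. All three samplers have the same correlation, although two of them are biased.

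**Step 3: spread between homes (s1 = 0.2, s2 = 0.5, no bias).** The ratio limits are exp(±1.96·√0.29) = 0.35 to 2.87 whatever the spread.

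- sT = 0.5: r = 0.25/√(0.29 × 0.50) = 0.66
- sT = 1.0: r = 1/√(1.04 × 1.25) = 0.88
- sT = 1.5: r = 2.25/√(2.29 × 2.50) = 0.94

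The error in a single home is the same in all three, yet r runs from 0.66 to 0.94.

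**Step 4: what a slope of 0.5 would do to an exposure contrast.** The Background cites a particulate reduction of about 50% with air purifiers. A sampler with a log-scale slope of 0.5 would turn a true ratio of 0.5 into 0.5^0.5 = 0.71, an apparent reduction of 29%. This borrows a PM figure for illustration; the protocol gives no corresponding figure for biomass.

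**The case against.** A reader might infer that the sampler is to be validated by correlation and that a poor device could therefore be declared usable. The documents do not support this. Validation is attached to usefulness and practicality in homes: "validate the utility of the Inspirotec sampler as easily deployable in home environments". Correlation, detection limits and deployability are listed as separate aims. No threshold or rule for accepting the sampler is stated, and interchangeability with PM10 sampling is not claimed.

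Three further objections have force:

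- **Units.** Neither method's biomass unit is given. If the units differ, a mean ratio or limits of agreement cannot be read as bias, and association is a reasonable first step. This limits which extra analysis applies. A calibration line with its prediction error remains available.
- **Imprecision.** Correlation is not blind to random error. With sT = 1 and s1 = 0.2, raising the sampler error SD to 1.0 lowers r to 1/√(1.04 × 2) = 0.69. A wide spread between homes can mask imprecision but does not remove its effect.
- **Pooling.** A reader might suppose that mixing arms and visits inflates r. The text does not say that they will be mixed. If the arms were pooled 1:1 with a 50% difference in level, the added variance would be (ln 2/2)² = 0.12, and the r of 0.80 would become 1.12/1.37 = 0.82, a small change.

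Finally, this is a two-sentence ancillary comparison that appears in neither the aims nor the outcomes. That argues for low priority. It does not supply the missing analysis.

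**Conclusion.** The point holds in a limited form and is minor. Correlation is the only stated analysis of the paired readings, and by itself it cannot show how well the sampler reproduces the PM10-based measure. That correlation misses a constant shift, and a slope change with matching error, follows from the formula and needs no assumed values. The sizes given (r = 0.80 with four-fold limits; r = 0.96 with a two-fold bias; r from 0.66 to 0.94 at the same precision) rest on assumed SDs and could differ in these homes. Those stated as ratios also assume a common unit.

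The trial's conclusions are untouched. The protocol states that "The primary outcome variable is the treatment step that the participant is assigned at the 6 month clinic visit", and neither that outcome nor the stated particulate and allergen analyses are described as using sampler data.

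**What to change.** Keep the correlation and label it descriptive. On the same paired data, prespecify:

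1. A log-scale calibration regression allowing error in both methods (for example Deming), reporting intercept, slope and prediction error for a single home. Deming regression needs the ratio of the two error variances. Unless duplicate samples are available, state the ratio assumed and show results over a range.
2. If both methods report in the same units, the mean ratio and 95% limits of agreement. If not, stop at the calibration line and its prediction error.
3. A random effect for home if any home contributes more than one visit.

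If the sampler is meant to stand in for PM10 sampling later, also state that intention, the number of homes and the agreement regarded as acceptable. The cost is a few lines of text and a little extra analysis, with no new samples or visits.

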Randomization: Participants will be randomized within 6 weeks (+/- 2 wks) of the screening clinic visit in a 1:1 ratio using a statistical software package to generate random numbers. The randomization scheme will be developed by the Data Management and Analysis Core (DMAC). Participants will be randomized in random block sizes of 4 to 8. The randomization scheme will be embedded into the recruitment/tracking database so that once a participant meets all eligibility criteria the site study coordinator can activate randomization through a secure user interface. The DMAC database programmer will have access to the computer code for the randomization scheme. Participants randomized to the ECS+Medication Group will be scheduled for an intervention prior to their next clinic visit.

ECS Intervention

Skin test data, home inspection data, and environmental history will be used to tailor an ECS to participants randomized to the ECS+Medication Group. Randomization will occur at CV1 and all of the information needed to assign ECS modules will have been collected before randomization. The 5 modules are listed below along with the qualifying criteria to receive the module and a summary of the components of each module (Table 5).

	Qualifying criteria	Components of Module
Rodent module	Positive skin test or IgE* to mouse or rat plus any evidence of infestation on home inspection OR parent report of evidence of infestation in the past month	Professional IPM Targeted cleaning IPM education Allergen-proof mattress and pillow encasements
Cockroach module	Positive skin test or IgE* to cockroach plus any evidence of infestation on home inspection OR parent report of evidence of infestation in the past month	Professional IPM Targeted cleaning IPM education Allergen-proof mattress and pillow encasements
Furry pet module	Positive skin test or IgE* to cat or dog	Education Allergen-proof mattress and pillow encasements Targeted cleaning
Dust mite module	Positive skin test or IgE* to dust mite	Education Allergen-proof mattress and pillow encasements Targeted cleaning
SHS module	Smoker in the home	Education
Air purifiers/Clean Bedding	None – everyone assigned to the ECS+medication arm will receive air purifiers and child’s bedding will be replaced with study bedding for study duration.	Deployment of 2 portable air purifiers, one in the child’s bedroom and one in the TV/living room. Child’s bedding will be replaced with study bedding for study duration.

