Air Purifiers will be provided to everyone randomized to the ECS + Medication Group as the targeted community is known to have high levels of PM_{2.5}, PM₁₀, and airborne mouse allergen. Portable HEPA purifiers with the same clean air delivery rate and performance characteristics of the purifiers used in our earlier studies will be used.^(12, 14) The purifiers will be suitable for use in rooms up to 17'x10', so will appropriate for use in rooms found in typical Baltimore housing. A random 10% sample of air filters will be monitored using electric current data loggers that record the presence of an electric current every hour in order to estimate air purifier use.

The first ECS module will be delivered between CV1 and CV2. Intervention 2, delivered only to those participants receiving the rodent and/or cockroach modules, will be delivered between CV2 and HV2. If possible, Intervention 3 will be delivered immediately following HV2 on the same day. If this is not possible, Intervention 3 will be delivered prior to CV3. Intervention 4 will be delivered between CV3 and CV4. At intervention visits, education

will be reinforced to participants randomized to the ECS+Medication Group to support the family's efforts in reducing allergen and pollutant exposures.

The Medication Group will receive skin test results at CV0 and educational materials about environmental control practices at CV1. The same educational materials will also be given to the ECS+Medication Group. The Medication Group will be offered the intervention after completion of the study with the exception of bedding being replaced. This visit is to be scheduled within 2 months of their last study visit.

All procedures and tests are part of the research protocol with the exception of study drugs, which are typically covered by health insurance.

b. Study duration and number of study visits required of research participants.

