Participants will be enrolled for approximately 7 months. There will be five clinic visits and three home visits over this time period for clinical and home assessments, respectively. There will be up to four environmental intervention visits for participants randomized to the environmental control plus controller medication group. Participants randomized to the controller medication group have the option of having one home visit after completing the study at which they will receive home intervention services that the environmental control plus controller medication group received with the exception of bedding being replaced.

c. Blinding, including justification for blinding or not blinding the trial, if applicable.

Participants will not be blinded because it is not practical and impossible to create a sham environmental intervention without exorbitant costs. The study physicians applying the treatment algorithm, which drives the primary outcome, will be blinded to the extent possible. For example, study staff will be trained not to divulge the participants' randomization group to the physician during the clinic visit.

d. Justification of why participants will not receive routine care or will have current therapy stopped. Participants will be asked to stop anti-histamines for approximately 5 days prior to skin testing at the screening visit since anti-histamines interfere with the skin test results. Otherwise, all participants will receive national guidelines-based titration of controller medication and education about asthma management.

e. Justification for inclusion of a placebo or non-treatment group.

Although there are two groups being compared in this trial, there is no group that is not receiving guidelines-based asthma treatment.

f. Definition of treatment failure or participant removal criteria.

A study participant will be discontinued from further study intervention if any clinical adverse event, other medical condition or situation occurs such that continued participation in the study would not be in the best interest of the participant.

This includes: (1) an asthma hospitalization that results in intubation and (2) a second asthma hospitalization during the course of the study.

g. Description of what happens to participants receiving therapy when study ends or if a participant's participation in the study ends prematurely.

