Participants may withdraw consent or be dropped from the study at any time. Every effort will be made to contact the participant by phone to conduct a final telephone interview. Participants will be referred back to their primary care provider (or subspecialist, if receiving subspecialty care) for asthma management.

All participants exiting the study after randomization without having received CV2 will be replaced.

4. Inclusion/Exclusion Criteria

Inclusion Criteria

- Males and females who are 5-17 years of age, inclusive, at the baseline visit
- Have physician-diagnosed asthma at least 1 year prior to the baseline visit, or asthma symptoms for at least 1 year
- Meet criteria for current persistent asthma defined as either:
 1. On a long-term controller medication for asthma, or
 2. Meet NAEPP guideline requirements for persistent disease:⁽⁶⁾
- Asthma symptoms 3 or more days per week over the past 2 weeks OR
- Nocturnal asthma symptoms at least 3 times in the past month
- Have evidence of uncontrolled disease as defined by at least one of the following:
 1. One asthma-related unscheduled visit to an emergency department (ED), clinic or urgent care facility in the previous 18 months
 2. One asthma-related overnight hospitalization in the previous 18 months
 3. One or more bursts of oral corticosteroids in the previous 18 months
- Reside within a geographic area of the study site so that home visits are feasible. • Have no plans to move within the upcoming 6 months
- Have insurance to cover prescription medications.
- Have a positive skin test (net wheal ≥ 2 mm) to cat, dog, mouse, rat, cockroach, or dust mites or have a positive cat, dog, mouse, rat, German cockroach, or *D. farinae*-specific IgE test, as quantified using the ImmunoCAP system (≥ 0.35 kU/L)

Exclusion Criteria

- Lung disease, other than asthma, that requires daily medication
- Cardiovascular disease that requires daily medication, excluding hypertension
- Taking a beta-blocker • Allergy to dairy
- On Xolair < 5 months
- On immunotherapy and has not reached maintenance dose
- Sleeping in another home 4 or more nights/week
- Active smoker defined as a positive urine screen for high levels of urine cotinine
- Unable to access areas of home necessary to conduct extermination • Pregnancy

5. Drugs/ Substances/ Devices

- a. The rationale for choosing the drug and dose or for choosing the device to be used.

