The power estimate is based on assessment of the primary outcome, treatment step, at 6 months. In the ICAS trial, the ECS resulted in a reduction of 0.8 symptom days/2 weeks within two months of randomization.⁽¹³⁾ The authors of the paper make the point that this effect size is similar to that seen with controller medications. In PREACH, the SHS intervention trial, there was an increase of 1.9 symptom-free days/2 weeks at six months in the group receiving air purifiers compared to the control group. This effect, which was observed with air purifiers alone and no other environmental intervention, is also similar in magnitude to low dose, inhaled corticosteroids, which resulted in an increase of 2 symptom-free days/2 weeks compared to placebo among children with persistent asthma (CAMP).⁽⁹⁾ With a multi-faceted intervention as proposed for this study, we expect a significantly larger effect size than observed with air purifier deployment alone. In terms of treatment step, low dose ICS is one “step-up” from no controller medication, which reflects the difference in controller medication requirement that our proposed study is powered to detect. Further, a 1 step reduction in controller medication requirement would also be the point at which an ECS would likely be cost effective. For example, in the ICAS trial,⁽¹³⁾ the intervention, which was effective for two years, cost approximately \$1500, similar to the cost of a one year supply of low dose ICS. There will be 7 possible treatment steps (Table 6) and, based on the distribution of participants across treatment steps in other studies, we will assume a mean treatment step of 4.0 at baseline among participants in both groups and have estimated the power to detect a difference of 1 treatment step between the two groups, with a standard deviation between 1.5 and 2. With a sample size of 200, and assuming alpha=0.05, we will have a power of 0.94 to detect a difference of this magnitude. With a drop-out rate of ~12%, there will be a power of 0.90. (Table 6)

Treatment step difference	SD	Power for n=200	Power for n=175
0.75	1.5	0.94	0.90
	2.0	0.75	0.69
1.00	2.0	0.94	0.90
	2.5	0.80	0.74

Analysis Plan

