The primary outcome will be the treatment step that is assigned at the final clinic visit at six months. The six month time point has been chosen because successful ECS trials have observed an effect by six months, but an effect may not be observed before this time because it takes several months for indoor allergen levels to fall after implementing an environmental intervention. The secondary outcome will be total daily ICS dose assigned at this same visit, expressed in milligrams. The primary analysis dataset will be an intent-to-treat (ITT) dataset and will include participants with six month outcome data collected, regardless of whether they completed all of the ECS activities. A per-protocol analysis will also be performed and will be performed on the dataset of participants with six month

outcome data who completed at least one intervention visit (one IPM visit or for the Medication Group, receipt of ECS educational materials). Exploratory data analysis for both Aims 1 and 2 will include compilation of descriptive statistics to detect any outliers or discrepancies in data and to compare baseline characteristics and demographics between ECS+Medication and Medication Groups. Continuous variables will be summarized using means, medians, standard deviations, ranges, and interquartile ranges. Continuous variables will be analyzed using non-parametric approaches or will be transformed to meet assumptions of normality required for parametric statistics. Categorical variables will be tabulated. The percent of participants who complete the study, losses to follow-up, missed visits, and reasons for discontinuation will be presented.

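### Children who leave between randomisation and CV2 are replaced and have no route into the intent-to-treat set, so the primary comparison is conditioned on staying after the arm is known

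*Combined protocol and SAP*

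**What the plan says.** All references are to the combined protocol and SAP.

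- **Study Procedures, item g (end of participation):** "All participants exiting the study after randomization without having received CV2 will be replaced". No distinction is made by arm or by reason. For children who leave, the plan offers this: "Every effort will be made to contact the participant by phone to conduct a final telephone interview". No timing is given.
- **Randomization:** allocation is 1:1 in random blocks of 4 to 8, activated by the coordinator once a child is eligible. "Participants randomized to the ECS+Medication Group will be scheduled for an intervention prior to their next clinic visit".
- **ECS Intervention:** "The first ECS module will be delivered between CV1 and CV2". The Medication Group is offered the intervention only after completing the study.
- **Study Procedures, item c (blinding):** "Participants will not be blinded because it is not practical". The physicians who apply the treatment algorithm "will be blinded to the extent possible".
- **Study Statistics, Analysis Plan:** the primary, intent-to-treat set "will include participants with six month outcome data collected, regardless of whether they completed all of the ECS activities". The per-protocol set also requires six-month data. Study completion, losses and reasons for discontinuation are to be presented, but not explicitly by arm.
- **Study Statistics, Power Estimate:** power is 0.94 with 200 children. "With a drop-out rate of ~12%, there will be a power of 0.90".

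The documents do not say how a replacement is allocated, whether a replaced child stays in any analysis population, whether 200 counts all randomised children or only those past CV2, or whether the ~12% includes early exits. They give no missing-data method for the primary outcome.

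**The concern.** Between CV1 and CV2 the arms have different experiences. Every ECS family receives air purifiers and has the child's bedding replaced. Depending on sensitisation and home findings, some also receive pest management, targeted cleaning, pet advice or smoking education. Medication families know they must wait. Arm-related reasons for leaving are therefore plausible in this window. Leaving may also be related to outcome: item f provides for discontinuation after certain asthma hospitalisations, and if that counts as exiting, a severe early course would be replaced.

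The primary outcome is the step assigned at the six-month clinic visit. A child who has left and is owed only a telephone interview has no stated way to supply it, and neither planned analysis set admits that child. The comparison is then between children who stayed once they knew their arm, which is not what intention to treat means. Refilling the sample makes this harder to see, because a count of 200 could describe either everyone randomised or only those who passed CV2.

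**Working it through.** **1. The plan's own power figures.** Inputs from the Power Estimate: difference 1 step, SD 2.0, alpha 0.05 (taken as two-sided), 1:1 allocation. Power ≈ Φ(Δ/SE − 1.96), with SE = SD × √(2/n per arm).

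- n = 100 per arm: SE = 0.283, 1/0.283 = 3.54, power 0.942 (stated 0.94).
- n = 87.5 per arm: SE = 0.302, 1/0.302 = 3.31, power 0.911; noncentral t gives 0.908 (stated 0.90).

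The stated figures reproduce.

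**2. Is replacement needed for power?** Early-exit rates are not in the documents and are assumed here. Take the less favourable reading, in which early exits come on top of 12% later loss. With 200 randomised and no replacement, the number analysed is 200 × (1 − e) × 0.88.

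| Early exit e | Analysed | Power (1 step, SD 2.0) |
|---|---|---|
| 0% | 176 | 0.913 |
| 5% | 167 | 0.898 |
| 10% | 158 | 0.882 |
| 15% | 150 | 0.864 |

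If the ~12% already includes early exits, power stays at the stated 0.90.

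**3. Bias from omitting early exiters.** Let e be the early-exit proportion in an arm, and D the exiters' mean six-month step minus the stayers' mean. The mean over all randomised children is the stayers' mean + e × D. For the ECS-minus-Medication difference, therefore:

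bias = (difference in stayers) − (difference in all randomised) = −(e_ECS × D_ECS − e_Med × D_Med).

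A negative value favours ECS. The number of replacements does not appear in the formula. Newly randomised children face the same exit risks, so they neither create nor remove the bias.

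Assumed cases, with 88 per arm and SD 2.0, so SE = 2 × √(2/88) = 0.30. Type I error = 1 − Φ(1.96 − b/SE) + Φ(−1.96 − b/SE).

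| Exit, ECS vs Medication | D | Bias (steps) | Type I error |
|---|---|---|---|
| 5% vs 5% | equal in both arms | 0 | 0.050 |
| 5% vs 2% | 0.5 to 2 in both arms | −0.015 to −0.06 | 0.050 to 0.055 |
| 10% vs 2% | 0.5 to 2 in both arms | −0.04 to −0.16 | 0.052 to 0.083 |
| 6% vs 6% | +1 ECS, −1 Medication | −0.12 | 0.068 |

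For 10% vs 2%: 0.08 × 0.5 = 0.04 and 0.08 × 2 = 0.16, or 0.13 to 0.53 SE. At SD 1.5, the lower end of the range in the Power Estimate text, SE = 1.5 × √(2/88) = 0.226, and a bias of 0.16 gives a type I error of 0.109. The signs reverse if D has the opposite sign. A more extreme split of 12% vs 0% with D = 2 gives −0.24 step.

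**4. The denominator.** If 200 means children past CV2, exits of 10% and 2% average 6%, so 200/0.94 ≈ 213 are randomised, about 106 per arm. Those past CV2 number 106.4 × 0.90 ≈ 96 in the ECS arm and 106.4 × 0.98 ≈ 104 in the Medication arm. A headline count of 200 would not show this.

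**The case against.** The strongest reply is that the replacement sentence is not the cause. Remove it and early exiters are still absent, because the Analysis Plan restricts the primary set to children with six-month data. This is correct, and it is why the two sections must be amended together.

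A reader might infer that replacement swaps randomised children for hand-picked ones, or that a replacement takes the vacated arm and so has a known allocation. The documents do not support either reading. They describe one way into the trial, 1:1 block randomisation of each eligible child. How a replacement is allocated is simply not stated, and a replacement is not known to be any likelier to stay.

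A reader might also infer that losses will be concealed. That goes too far as well, since losses and reasons are to be presented. What is missing is a commitment to do so by arm and to count replaced children.

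Other mitigating facts stand. Modules are tailored, so only purifiers and bedding reach every ECS family. Screening for planned moves, access to the home and very low adherence removes some likely early leavers. The physicians who assign the step are blinded as far as possible, although this does not affect a family's decision to leave. Finally, a regimen reported by telephone after care has returned to the child's own provider is not the algorithm-assigned step, so it can serve only as a proxy.

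**Conclusion.** The concern holds in this limited form: replacing pre-CV2 exits and restricting the intent-to-treat set to six-month data together condition the primary comparison on staying after the arm is known, and leave the randomised denominator undefined. Bias requires exit rates, or exiters' outcomes relative to stayers', to differ between arms. With assumed exits of 10% and 2%, and exiters 0.5 to 2 steps away from stayers, it is about 0.04 to 0.16 step, or 4% to 16% of the 1-step target. It is zero if exit rates and exiters' outcomes are alike in both arms. Neither its sign nor its actual size can be determined from the documents. This is modest and would not by itself overturn a true 1-step effect, but it is avoidable, and replacement is not needed to keep power close to 0.90. The change is worth making on grounds of low cost rather than large expected bias.

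**What to change.** Amend Study Procedures item g and the Analysis Plan together.

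- **(a) Population.** All randomised children stay in their assigned arm, in the intent-to-treat population and in the participant flow, whenever they leave.
- **(b) Additional children.** Any child added to offset early loss enters only by the next allocation in the existing block sequence. State whether 200 means all randomised or those past CV2, and whether the ~12% includes early exits.
- **(c) Contact.** Time the telephone contact already planned at month 6, where consent permits, and record the child's current controller regimen.
- **(d) Sensitivity analysis.** Supplement the primary analysis with one of all randomised children. Use the telephoned regimen as a proxy for the Table 3 step, and multiple imputation or a delta adjustment for children who cannot be reached.
- **(e) Reporting.** Present exits before CV2 by arm, with reasons.

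The cost is a short text amendment, an added analysis and a few telephone calls. There are three drawbacks. The proxy is self-reported by families who know their arm and is not the algorithm-assigned step; some families who withdrew may not be contactable; and reported retention will look slightly lower.
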